#### 4. Analysis Populations

Screen failure subjects will not be included in any analyses.

Subjects who start any of the study drugs (i.e., axitinib or placebo) will be considered to have started treatment.

##### 4.1. Intent-To-Treat Population

Intent-to-Treat (ITT) Population: This population will include all randomized subjects regardless of whether or not treatment was administered and will be based on randomized treatment assignment. This population will be the primary population for evaluating baseline characteristics and efficacy.

##### 4.2. As-Treated Population

As-Treated (AT) Population: The As-Treated population consists of all subjects who received at least 1 dose of study medication with treatment assignments designated according to actual study treatment received. This population will be the primary population for evaluating treatment administration/compliance and safety.

The number and percentage of subjects in each population will be summarized by treatment group and listed.

##### 4.3. Treatment Misallocations

If subjects were:

- Randomized but not treated, then they will be reported under their randomized treatment group for efficacy analyses. However, they are by definition excluded from the safety analyses as actual treatment is missing.
- Randomized but took incorrect treatment, then they will be reported under their randomized treatment group for all efficacy analyses, but will be reported under the treatment they actually received for all safety analyses.

A summary table of treatment misallocations will be provided.

##### 4.4. Protocol Deviations

---

|           |   |                 |           |
|-----------|---|-----------------|-----------|
| Document: | C:\Users\q764206\AppData\Local\Microsoft\Windows\Temporary Internet Files\Content.Outlook\GWW33WM3\ATLAS_SAPFinal v8.0_06MAR2018.docx |                 |           |
| Author:   | [name] (Updated [name]; [name]; [name], [name])  | Version Number: | Final 8.0 |
|           |   | Version Date:   | 06MAR2018 |

Template No: CS\_TP\_BS016 – Revision 2  
Effective Date: 01Feb2010

Reference: CS\_WI\_BS005

Statistical Analysis Plan

---

Subjects with major protocol deviations will be summarized by treatment group.

Major protocol deviations include, but are not limited to:

- Subjects who did not meet inclusion/exclusion criteria or eligibility was not adequately verified
- Received prohibited concomitant medications post-baseline
- Developed withdrawal criteria but were not withdrawn
- Has a dosing error likely to impact key outcome measures (for example subject did not receive the medication they were randomized to receive)

## 5. Efficacy Endpoints and Covariates

### 5.1. Primary Efficacy Endpoint

The primary endpoint is DFS, defined as the time interval (measured in years) from the date of randomization to the first date of recurrence (distant or local recurrence of RCC) or the occurrence of a secondary malignancy or death due to any cause. The primary DFS analysis will be based on assessment by the IRC. The IRC will review all available scans and in cases for which there is site confirmation of recurrence or occurrence of a secondary malignancy in the absence of IRC imaging confirmation, available local histo-/cytopathology reports will be reviewed by an independent IRC oncologist.

Recurrence refers to relapse of the primary tumor in situ or at metastatic sites. The date of recurrence or the occurrence of a secondary malignancy is defined as the earlier of:

- the date of the tumor scan or the date of collection of the histo-/cytopathological specimen (for subjects who have site confirmed recurrence or occurrence of a secondary malignancy in the absence of IRC imaging confirmation) that demonstrated unequivocal recurrence or a second malignancy according to protocol criteria

Per the IRC charter, radiological findings should be unequivocal. At the time of the final IRC review for a given data cut (interim or final), equivocal disease, identified by radiology requiring confirmation, is noted in the IRC data at the ‘Global Review’ with an indication of disease present and a date of recurrence/secondary malignancy recorded by the IRC as not applicable (N/A). As these findings require confirmation, they will not be counted as events in the DFS analysis unless, there is a subsequent pathology report which provides confirmation of the disease seen on the scan. In this case the scan date should be used as the date of recurrence or secondary malignancy.

In the absence of pathology to confirm the equivocal findings, these subjects will be censored at the date of last scan before anti-cancer therapy (if applicable). The last scan date includes the scan where the equivocal finding was noted.

For subjects identified as having the presence of disease at baseline by IRC review,

- Recurrence will be considered to have occurred on the date of randomization.

---

|           |   |                 |           |
|-----------|---|-----------------|-----------|
| Document: | C:\Users\q764206\AppData\Local\Microsoft\Windows\Temporary Internet Files\Content.Outlook\GWW33WM3\ATLAS_SAPFinal v8.0_06MAR2018.docx |                 |           |
| Author:   | [name] (Updated [name]; [name]; [name], [name])  | Version Number: | Final 8.0 |
|           |   | Version Date:   | 06MAR2018 |

Template No: CS\_TP\_BS016 – Revision 2  
 Effective Date: 01Feb2010

Reference: CS\_WI\_BS005

Statistical Analysis Plan

---

For subjects with no DFS event, DFS time will be censored

- at the date of last IRC reviewed scan prior to the time of the final analysis.
- Subjects alive who do not have any post-baseline disease assessments will have their DFS times censored at randomization.

For any subject who receives anti-tumor therapy,

- DFS will be censored on the date of the last IRC reviewed scan prior to taking the anti-tumor therapy. However, in cases where there is no scan prior to anti-cancer therapy medication that was received after randomization, subjects will be censored at the date of randomization.

For subjects who had two or more consecutively missed or not readable IRC reviewed scans immediately prior to a recurrence or occurrence of a secondary malignancy or death,

- DFS will be censored on the date of the last IRC reviewed scan prior to the consecutively missed or not readable IRC reviewed scans.

The length of DFS will be calculated as follows:

$$\text{DFS (years)} = [\text{date of recurrence, secondary malignancy, or death or censor date} - \text{randomization date} + 1] / 365.25.$$

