**7. Statistical Analysis**

**7.1. Analysis of Primary Efficacy Endpoint**

**7.1.1. Disease-Free Survival Based on IRC Review**

Disease-Free Survival of the ITT Population based on the IRC review of tumor assessments will be summarized using the Kaplan-Meier method. Kaplan-Meier curves for each arm will be generated, and median DFS time will also be presented with corresponding 95% CI. The CI for the median will be calculated according to Brookmeyer and Crowley. To test the equality of DFS time in each arm a stratified log-rank test (using a stratification factor as defined in Section 5.4) will be used. Censoring rules as described in Table 1 of Appendix A will be implemented. The statistic of the test will be presented along with the associated two-sided p-value.

The estimated HR (Axitinib/Placebo) will be obtained using a Cox’s Proportional Hazards model with treatment group as well as a randomization stratification factor as a covariate. The stratification factor used in the analyses will be risk group as described in Section 5.4.1.

The significance level for the final DFS analysis will be 0.0442 as calculated using the O’Brien-Fleming method. (Assumes interim analysis at 184 events with a significance level of 0.0194).

Annual DFS rates up to 5 years for each treatment group will be estimated and presented with corresponding 95% CI. The CI for the survival function will be calculated using the complementary log-log transformation method.

The final analysis of the primary endpoint of DFS will be performed when approximately 245 DFS events based on IRC review are observed.

A subject listing for DFS will include, DFS time, censoring status, censoring reason, date of randomization and date of last tumor assessment. In addition, a listing of subjects with baseline disease as determined by the IRC, will be produced.

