**Statistical Analysis Plan**

---

a3: number of times agreement on event but INV declares event earlier than IRC Review;  
 $N = a+b+c+d$ .

The following measure of discordance will be calculated per arm:

- Total Event Discrepancy Rate:  $(b+c) / N$
- Early Discrepancy Rate (EDR):  $(a3+b) / (a+b)$
- Late Discrepancy Rate (LDR):  $(a2+c) / (a2+a3+b+c)$
- Overall Discrepancy Rate:  $(a2+a3+b+c) / N$

A window of 28 days will be used in determining agreement on timing of an event. Specifically, if the data or recurrence by the IRC is within +/- 28 days of the data of recurrence by the investigator these cases will be considered as ‘agreement on the timing and occurrence or an event’.

- DFS based on IRC Without Censoring for New Cancer Therapy or Missed Assessments: DFS based on IRC review, as defined for the primary analysis, but without censoring subjects who:
  - receive further anti-tumor therapy, or
  - have two or more consecutively missed or not readable scans immediately prior to recurrence, or occurrence of a secondary malignancy, or death.

In other words, a subject who meets the above criteria will be assigned a DFS event at the first date of recurrence or occurrence of a second primary cancer or death. In the absence of a DFS event, DFS time will be censored at the date of last scan prior to the time of analysis. Subjects alive who do not have post-baseline disease assessment will have their DFS times censored at randomization. (Refer to Table 4 of Appendix A for censoring rules.)

- Start of New Anti-tumor Therapy as DFS Event: DFS based on IRC review, as defined for the primary analysis, but utilizing the start date of new anti-tumor therapy as a DFS event. (Refer to Table 5 of Appendix A for censoring rules.)
- DFS at Scheduled Assessments: DFS based on IRC review, as defined for the primary analysis, but instead assigning the dates for events and censoring at the scheduled scan dates instead of the actual scan dates. Specifically, events that occur within +/- 4 weeks of a scheduled scan will be considered an event at the scheduled scan. Events outside the 4-week window will be counted as events at the next scheduled scan time and censoring outside the 4-week window would be censored at the previous scheduled scan. If, however, the event is death or disease at baseline, the date of death or date of randomization respectively will be used as the event date unless anti-tumor therapy was

---

|           |   |                 |           |

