**7.3.4. Exploratory Analyses**

Exploratory analyses may be performed as deemed appropriate.

RMST for DFS may be explored if non-proportional hazards are observed for the primary endpoint.

DFS and Treatment Duration: A one-year landmark analysis will be performed to explore the association between extended treatment with Axitinib and DFS. Patients randomized to Axitinib will be divided into 2 groups based on treatment status at 1 year. Namely patients whose duration of treatment in less than or equal to one year will be compared to those whose duration of treatment is greater than one year. Only patients randomized to treatment with Axitinib who are alive, disease-free, and still in disease-free survival follow-up at one year will be included in the analysis. Specifically, patients who had disease recurrence, secondary malignancies, died, or were otherwise censored for DFS due to start of new anticancer therapy, missed assessments, or lost to follow-up prior to one year will be excluded from the analysis. Median event times and 2-sided 95% CIs for each median will be provided based on the Brookmeyer-Crowley method. Cox proportional hazards model will be used to estimate the unstratified hazard ratio and its 95% CI. A p-value will not be reported as this analysis is considered exploratory.

Treatment Discontinuations due to AEs of Interest: an evaluation of cumulative incidence of treatment discontinuations for defined AEs of interest will be conducted. A summary table will be provided. A figure displaying the proportion of subjects off treatment over time will be provided for subjects randomized to axitinib or placebo who experienced various defined adverse events of interest.

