## 9. Appendix A

**Table 1. Primary Endpoint Disease-Free Survival by Independent Review Committee Censoring Rules:**

|  |  | Date of event*/ censoring  | Censoring |
|--|--|---|------------------|
| No IRC confirmed recurrence or occurrence of secondary malignancy or death | Post baseline assessments performed  | Date of last IRC reviewed scan prior to receiving anti-tumor therapy, if applicable   | Yes              |
|  | No post baseline assessments performed   | Date of randomization   | Yes              |
| IRC confirmed recurrence, secondary malignancy or death                    | Baseline scan shows presence of disease  | Date of randomization   | No               |
|  | Further anti-tumor therapy received after randomization and before recurrence or occurrence of secondary malignancy or death (Subject does not have two or more consecutively missed/not readable IRC reviewed scans immediately prior to recurrence, secondary malignancy or death)** | Date of last IRC reviewed scan prior to receiving anti-tumor therapy  | Yes              |
|  | Further anti-tumor therapy received after randomization and before recurrence or occurrence of secondary malignancy or death and subject had two or more consecutively missed/not readable IRC reviewed scans immediately prior to recurrence, secondary malignancy or death)**        | Date of last IRC reviewed scan prior to the two consecutively missed/not readable scans and prior to receiving anti-tumor therapy** | Yes              |
|  | No anti-tumor therapy received after randomization (Subject does not have two or more consecutively missed/not readable IRC reviewed scans immediately prior to recurrence, secondary malignancy or  | Date of IRC confirmed recurrence or occurrence of secondary malignancy or death, whichever occurred first*                          | No               |

Document: C:\Users\q764206\AppData\Local\Microsoft\Windows\Temporary Internet Files\Content.Outlook\GWW33WM3\ATLAS\_SAPFinal v8.0\_06MAR2018.docx

Author: [name] (Updated [name]; [name]; [name], [name])

Version Number:

Final 8.0

Version Date:

06MAR2018

Template No: CS\_TP\_BS016 – Revision 2  
 Effective Date: 01Feb2010

Reference: CS\_WI\_BS005

Statistical Analysis Plan

|  |  |   |     |
|--|--|---|-----|
|  | death)**   |   |     |

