**Table 3. Sensitivity Analysis Disease-Free Survival by Investigator Assessment Censoring Rules:**

|   |   | Date of event/ censoring  | Censoring |
|---|---|---|-----------|
| No Investigator confirmed recurrence or occurrence of secondary malignancy or death | Post baseline assessments performed               | Date of last local imaging assessment prior to receiving anti-tumor therapy if applicable | Yes       |
|   | No post baseline assessments performed            | Date of randomization   | Yes       |
| Investigator confirmed  | Baseline scan evaluated by the investigator shows | Date of randomization   | No        |

Document: C:\Users\q764206\AppData\Local\Microsoft\Windows\Temporary Internet Files\Content.Outlook\GWW33WM3\ATLAS\_SAPFinal v8.0\_06MAR2018.docx  
 Author: [name] (Updated [name]; [name]; [name], [name]) Version Number: Final 8.0

Version Date: 06MAR2018

Template No: CS\_TP\_BS016 – Revision 2 Reference: CS\_WI\_BS005  
 Effective Date: 01Feb2010

Statistical Analysis Plan

|   |   |  |     |
|---|---|--|-----|
| recurrence or secondary malignancy or death | presence of disease   |  |     |
|   | Further anti-tumor therapy received after randomization and before recurrence or occurrence of secondary malignancy or death (Subject does not have two or more consecutively missed local imaging assessments immediately prior to recurrence, secondary malignancy or death)* | Date of last local imaging assessment prior to receiving anti-tumor therapy  | Yes |
|   | Further anti-tumor therapy received after randomization and before recurrence or occurrence of secondary malignancy or death and subject had two or more consecutively missed local imaging assessments immediately prior to recurrence, secondary malignancy or death)*        | Date of last local imaging assessment prior to the two consecutively missed scans and prior to receiving anti-tumor therapy* | Yes |
|   | No anti-tumor therapy received after randomization (Subject did not have two or more consecutively missed local imaging assessments)*   | Date of investigator confirmed recurrence or occurrence of secondary malignancy or death, whichever occurred first           | No  |
|   | No anti-tumor therapy received after randomization but subject had two or more consecutively missed local imaging assessments*  | Date of last local imaging assessment before two consecutively missed local imaging assessments*                             | Yes |

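### Does counting disease seen by the IRC at baseline as a DFS event at randomization, with no planned IRC comparison that leaves these subjects out, weaken the DFS analysis?

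*SAP*

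**What the plan says.** SAP 5.1 defines DFS by IRC assessment and says of subjects with disease at baseline on IRC review: "Recurrence will be considered to have occurred on the date of randomization". In Appendix A, the row "Baseline scan shows presence of disease" is an uncensored event at randomization in Table 1 (primary analysis), and it recurs in Tables 4, 5, 6 and 7, the four IRC-based sensitivity analyses. The text of SAP 7.3.1 on scheduled assessments agrees: where "the event is death or disease at baseline, the date of death or date of randomization respectively will be used". Table 3, for investigator-assessed DFS, has a parallel row that begins "Baseline scan evaluated by the investigator shows" and relies on the investigator's own reading.

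The analysis population is intent-to-treat: "This population will include all randomized subjects regardless of whether or not treatment was administered" (SAP 4.1). Three other provisions touch these subjects:

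- SAP 7.1.1: "a listing of subjects with baseline disease as determined by the IRC, will be produced".
- SAP 4.4 summarizes major deviations by treatment group, among them "Subjects who did not meet inclusion/exclusion criteria or eligibility was not adequately verified".
- The one-year landmark analysis in SAP 7.3.4 drops them, but it covers one arm: "Only patients randomized to treatment with Axitinib who are alive, disease-free, and still in disease-free survival follow-up at one year".

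SAP 6.3 applies the futility boundary to IRC-assessed DFS only and makes it non-binding.

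**The concern.** Disease already visible before randomization cannot be prevented by adjuvant treatment. Each such subject adds an event to the counts of 184 and 245 but carries no information about the drug. On average these events move the hazard ratio toward 1, and a chance imbalance between the arms can move it either way.

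The same row appears in every IRC-based censoring table, so those sensitivity analyses all share the feature and none can isolate it. The subgroups in SAP 7.3.2 do not include baseline disease, and the restricted-mean analysis in SAP 7.1.2 uses the same DFS data. If the IRC result were weak, or crossed the futility boundary, no planned comparison would show directly whether disease present at entry had contributed. The SAP also does not say whether readers may use later scans when they assign the baseline label.

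**Working it through.** **Inputs.** HR 0.654, 245 events, 90% power and two-sided 0.05 (SAP 3.3). Interim at 184 events, two-sided boundaries 0.0194 and 0.0442, futility p 0.2255 (SAP 6.3). The number of baseline-disease subjects, k, is in neither document, so k = 0, 2, 5 and 14 are assumed (0 to 2% of 700).

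**The plan's own figures.**

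- Freedman's formula: [(1.960 + 1.282) × 1.654 / 0.346]² = 240.1. Multiplied by 1.017 for one O'Brien-Fleming-type look at 184/245, this is 244.2, rounded up to 245.
- The boundaries correspond to z = 2.338 (interim efficacy), 2.012 (final) and 1.212 (futility).
- exp(−2z/√D) gives 0.708 and 0.836 at D = 184, and 0.773 at D = 245. All three match the SAP tables.

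**Effect of k events at randomization.** At that moment everyone is at risk and the arms are about 1:1. Such an event therefore adds variance to the log-rank statistic but no expected treatment difference. With θ = −ln 0.654 = 0.4246:

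- mean Z, subjects kept as planned: θ(D − k)/(2√D)
- mean Z, subjects left out at the same cut-off: θ√(D − k)/2

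At k = 5 and D = 184 the kept mean is 0.4246 × 179/(2 × 13.565) = 2.802, against 2.880 at k = 0. The chance of crossing futility is Φ(1.212 − 2.802) = 5.6%, against Φ(1.212 − 2.880) = 4.8%.

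Power below is the probability of crossing either efficacy boundary, without a futility stop. The correlation between looks is √(184/245) with the subjects kept and √((184 − k)/(245 − k)) without them.

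| k | Power, kept | Power, left out | Futility, kept | Futility, left out |
|---|---|---|---|---|
| 0 | 90.9% | 90.9% | 4.8% | 4.8% |
| 2 | 90.5% | 90.7% | 5.1% | 4.9% |
| 5 | 89.7% | 90.3% | 5.6% | 5.2% |
| 14 | 87.3% | 89.3% | 7.4% | 6.0% |

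The average HR at 245 events is about 0.654^((245 − k)/245): 0.660 at k = 5 and 0.670 at k = 14.

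**Type I error.** The rule is the same in both arms. If the label rests on pre-randomization images, it is fixed before assignment. With no treatment effect, these events fall evenly between the arms in expectation.

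**Is the date the cause?** A simulation used 4,000 trials per cell, 700 subjects, the SAP event and dropout rates, random assignment and the risk-group-stratified log-rank test. It compared an event at randomization with an event at week 16 that carries no treatment effect. Power was 90.4% against 90.3% at k = 5, and 87.9% against 88.6% at k = 14. The standard error is about 0.5 point per cell, so a difference has a standard error of about √(0.5² + 0.5²) = 0.7 point. The date makes no detectable difference. The dilution comes from having these subjects in the intent-to-treat population.

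**Would the extra analysis change a decision?** In the same simulation at k = 5, the planned analysis crosses futility while the exclusion analysis does not in 1.0% of trials, and the reverse happens in 0.6%. They disagree in 1.6% in total. At k = 14 the figures are 2.6% and 0.9%, or 3.5% in total.

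**How many cases are plausible?** Absence of macroscopic residual or metastatic disease is inclusion criterion 1 (Protocol 4.1). IRC imaging results must be awaited before randomization (Protocol 6.1.1). The IRC reading decides when it differs from the local one (Protocol 4.3). Brain images are the stated exception, since they go for retrospective confirmation (Schedule of Assessments, footnote 13). Cases should therefore come mainly from brain findings, departures from the procedure, or later re-reading.

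**The case for a change.** The best argument for adding the analysis is credibility. An exclusion named in advance is more convincing than one chosen after a borderline result, and it costs one extra run at each of two looks. Investigator-assessed DFS is no clean substitute, because it changes the assessor as well as the handling of these cases. The SAP also finds the situation likely enough to give it a rule, a row in each IRC table and a listing. If cases were numerous the effect would be material. With 40 of 245 events (5.7% of 700 subjects), the average HR would be 0.701, and power at the final look alone would fall from 90.5% to 78.3%, or 84.8% with those subjects left out.

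The textual points stand: the rule is in all five IRC tables, and no two-arm IRC comparison omits these subjects. The rest does not amount to a fault. Nothing in the documents supports a count near 40. A supportive analysis with no alpha leaves the trial's power and its futility probability where they are. The difference between the kept and left-out columns is a property of a test that decides nothing, so the benefit would be interpretive only.

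The question about the label stays open, but it cannot be counted as an omission. SAP 5.1 refers to the IRC charter for reading conventions, and the charter is not available here. If the label is the reading made before randomization, the excluded group should be nearly empty. If it comes from later re-reading, a clean exclusion might need new blinded reads. If later scans can inform it, leaving these subjects out would condition on information gathered after randomization.

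**Conclusion.** The concern does not hold. Keeping these subjects in the primary analysis follows from intent-to-treat, the dating rule makes no detectable difference, and Type I error is not inflated. With 2 to 5 cases, power falls by about 0.4 to 1.2 points and the chance of crossing a non-binding futility boundary rises by about 0.3 to 0.8 point. A comparison without these subjects would change neither figure.

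The listing identifies the subjects, eligibility failures are summarized by arm, and discordance between IRC and investigator is tabulated per arm (SAP 7.3.1). SAP 7.3.4 permits exploratory analyses, so analysts can run the exclusion if the listing proves long. Naming it in advance is a matter of preference, not a correction.

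The conclusion assumes that the IRC review before randomization works as the protocol describes, so that cases are few, and that the baseline label does not draw on later scans. The documents do not let either assumption be checked.

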## 6.4. Recurrence or occurrence of secondary malignancy and Survival Follow-Up

Follow-up for recurrence or occurrence of a secondary malignancy must be collected at each clinic visit as per protocol. All patients will be followed up (regardless of the duration of treatment) until the time for final analysis, every 16 weeks for the first 3 years from initiation of study treatment (also, at the end of treatment) and every 6 months thereafter for the remainder of follow-up period\*. If new anti tumor therapy is initiated for either recurrence or occurrence of a secondary malignancy at any time during this period, this and all other pertinent data obtained should be recorded on the appropriate CRFs. The final analysis of primary endpoint (DFS) will be performed when approximately 245 DFS events have been reached.

\* Patients who complete 3-year treatment will be followed up for DFS every 6 months from the date of CT or MRI at the end of study treatment.

Patients who withdraw from treatment before DFS events will be followed up for DFS every 16 weeks from the date of CT or MRI at the withdrawal. After 3 years from initiation of study treatment, CT or MRI for DFS will be performed every 6 months from the first scan date that is performed after more than 3 years from initiation of study treatment.

All patients will be followed up for OS status (regardless of the duration of treatment) approximately every 16 weeks from DFS events until the time for final DFS analysis. Survival status can be ascertained by telephone contact.

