## 7.1.1. Primary Endpoint

DFS is defined as the time interval from the date of randomization to the first date of recurrence (distant or local recurrence of RCC) or the occurrence of a secondary malignancy or death. The primary DFS analysis will be based on assessments by the IRC. IRC will review all imaging data. Additionally, in cases for which there is site confirmation of recurrence or occurrence of a secondary malignancy in the absence of IRC imaging

confirmation, available local histo-/cytopathology reports will also be reviewed by the IRC oncologist to determine confirmation of recurrence or occurrence of a secondary malignancy.

Recurrence refers to relapse of the primary tumor in situ or at metastatic sites. The date of recurrence or the occurrence of a secondary malignancy is defined as the date of the tumor scan or the date of collection of the histo-/cytopathological specimen (for patients who have site confirmation of recurrence or occurrence of secondary malignancy in the absence of IRC imaging confirmation) that demonstrated unequivocal recurrence or a secondary malignancy according to protocol criteria. If both imaging and histo-/cytopatholigical confirmation of recurrence or sencondary malignancy are available, the earlier of the two dates will be considered.

For patients with no DFS event, DFS time will be censored at the date of the last scan prior to the time for the analyses. Patients alive who do not have post-baseline disease assessments will have their DFS times censored at randomization. For patients receiving further anti-tumor therapy prior to recurrence or occurrence of a secondary malignancy or death, DFS will be censored on the date of the last scan prior to taking the anti-tumor medication. Patients who miss 2 or more consecutive tumor scans immediately followed by an event will be censored at the date of the last objective tumor assessment prior to the missing/not readable scans.

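### SAP 5.1 censors for anti-tumor therapy with no limit to therapy before the event, and Tables 1 and 3 have no row for a recurrence treated after it is confirmed

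*SAP*

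**What the plan says.** Protocol 7.1.1, repeated in the protocol summary, ties the censoring to the order of therapy and event: "For patients receiving further anti-tumor therapy prior to recurrence or occurrence of a secondary malignancy or death, DFS will be censored" at the last scan before the medication. Protocol 6.4 expects therapy after an event as well, and asks for it to be recorded: "If new anti tumor therapy is initiated for either recurrence or occurrence of a secondary malignancy at any time during this period".

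SAP 5.1 states the rule without the ordering. It begins "For any subject who receives anti-tumor therapy" and continues "DFS will be censored on the date of the last IRC reviewed scan prior to taking the anti-tumor therapy". The next rule in the same list, on missed scans, does carry a timing limit relative to the event.

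For the primary test, SAP 7.1.1 states: "Censoring rules as described in Table 1 of Appendix A will be implemented". In Table 1 the two rows that censor for therapy keep the limit: "Further anti-tumor therapy received after randomization and before recurrence or occurrence of secondary malignancy or death". The only row that counts a post-baseline event has no end point on its therapy condition: "No anti-tumor therapy received after randomization (Subject does not have two or more consecutively missed/not readable IRC reviewed scans". The matching event row of Table 3 reads: "No anti-tumor therapy received after randomization (Subject did not have two or more consecutively missed local imaging assessments".

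SAP section 1 says that the SAP supersedes the protocol, and that major changes to the primary endpoint will appear in a protocol amendment. The account of Amendment 10 in SAP 3.4.2 mentions no change to this rule.

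**The concern.** Treatment after a recurrence is an ordinary course in this setting. As written, the SAP gives such a patient either no outcome (Table 1) or the opposite outcome to the protocol (the 5.1 therapy sentence). Two programmers could derive different event counts from the same data, one from the 5.1 therapy sentence and one from the DFS definition at the start of 5.1.

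Three things depend on the answer:

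- The interim and final analyses are triggered by IRC-assessed events, 184 and 245.
- The primary log-rank test would treat true recurrences as censored. That censoring is informative, because the recurrence is what leads to the therapy.
- Under SAP 6.3, investigator-assessed DFS must also cross the interim efficacy boundary (two-sided p below 0.0194 at 184 IRC events). The gap in Table 3 therefore bears on a stopping decision and not only on a sensitivity analysis.

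**Working it through.** **1. The plan's event number.** The overall hazard ratio is the weighted mean of the three category values: 0.90 × 0.66 + 0.01 × 0.47 + 0.09 × 0.61 = 0.6536, stated as 0.654. Freedman's formula gives (1.960 + 1.282)² × (1.654/0.346)² ≈ 240.1, so 241 events, within 3% of the stated 245. Schoenfeld's formula gives 234. With the Lan-DeMets O'Brien-Fleming look at 75%, 245 events give 90.9% power, or 89.9% if the futility boundary is also followed. The 245 is therefore sound, provided that true events are counted as events.

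**2. The test case against Table 1.** Take an IRC-confirmed post-baseline recurrence, no missed scans, with anti-tumor therapy started afterwards. The confirmed-event block has five rows.

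| Row (paraphrased) | Outcome | Does the case fit? |
|---|---|---|
| Disease on the baseline scan | Event | No, the recurrence is post-baseline |
| Therapy before the event, no missed scans | Censored | No, therapy came after |
| Therapy before the event, missed scans | Censored | No, therapy came after |
| No therapy after randomization, no missed scans | Event | No, therapy was received |
| No therapy after randomization, missed scans | Censored | No, therapy was received |

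No row applies. Table 3 has the same five rows and the same gap. The only SAP rule whose words reach the therapy is the 5.1 sentence, and it censors.

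**3. What the literal rule does to one patient.** SAP 5.1 gives DFS in years as (date − randomization date + 1)/365.25. The dates below are assumed, placed on the 16-week scan schedule.

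- Week 48: (336 + 1)/365.25 = 0.923
- Week 56: (392 + 1)/365.25 = 1.076
- Week 64: (448 + 1)/365.25 = 1.229

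| Case | Protocol | Literal 5.1 |
|---|---|---|
| A. Recurrence scan week 48, therapy before the next scan | Event, 0.923 | Censored, 0.923 |
| B. Recurrence dated to week 48, further scan at week 64, then therapy | Event, 0.923 | Censored, 1.229 |
| C. Recurrence by pathology only, specimen week 56, last IRC scan week 48, then therapy | Event, 1.076 | Censored, 0.923 |

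Case B needs late confirmation. One route is an equivocal finding confirmed by later pathology, where SAP 5.1 uses the scan date. Protocol 7.1 keeps patients on assessments until the IRC determines the event. In all three cases one event leaves the count.

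**4. Room in the event count.** Inputs from SAP 3.3: 700 subjects 1:1, the three categories with their 2-year DFS rates, 24 months' accrual, 60 months in total, and 23% drop-out by 18 months. Uniform accrual and exponential drop-out are added assumptions. The event hazard is λ = −ln(2-year rate)/24 and the drop-out hazard is η = −ln(0.77)/18 = 0.0145 per month. The event probability is λ/(λ+η) × [1 − exp(−(λ+η)(60−u))], averaged over entry time u from 0 to 24. Expected events by month 60 are 144.6 on placebo and 106.6 on axitinib, 251.3 in all. The margin over 245 is 6.3 events, or 6.3/251.3 = 2.5%.

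The share f of events that are treated afterwards is not in the documents. If f were 10%, 30% or 50%, the true events needed to count 245 would be 245/(1−f) = 272, 350 or 490.

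**5. Direction of bias.** If a constant share of events is lost in each arm, the apparent hazard ratio is the true one × (1−f on axitinib)/(1−f on placebo). Equal shares leave 0.654. Assumed shares of 50% on axitinib and 60% on placebo give 0.654 × 0.5/0.4 = 0.82; the reverse gives 0.654 × 0.4/0.5 = 0.52. The direction cannot be known in advance.

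**The case against.** The strongest reply is that the intended rule is plain. SAP 7.1.1 points to Table 1, and Table 1 censors for therapy only when it precedes the event. Apart from baseline disease, its confirmed-event rows form a two-by-two grid of therapy by missed scans, so the no-therapy rows can be read as the complement of the therapy rows. The table's second footnote, on deaths, limits its therapy condition to the time before death. Protocol 9.2.1 and the therapy rows of SAP Table 5 also place therapy before the event. SAP section 1 promises an amendment for any major change to the primary endpoint, and none is listed. A literal use of 5.1 should also come to light, because the DFS listing gives each subject's censoring reason and Table 4 counts events regardless of therapy.

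Most of this stands as evidence of intent. It does not remove the contradiction. The complement reading has to supply words that the event row lacks. The footnote covers deaths, not treated recurrences. SAP section 1 also says that the SAP supersedes the protocol. The listing and Table 4 could reveal an error after derivation, but they do not define the primary event.

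Two cautions are fair. Appendix B calls an event inside the missed-scan window non-censored without mentioning therapy, but it deals only with missed scans and is weak evidence on this point. The landmark text in SAP 7.3.4, which lists recurrence apart from censoring for new therapy, is loosely worded. The finding does not depend on either.

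**Conclusion.** The concern holds. SAP 5.1 drops a limit that the protocol sets on the primary endpoint, and the event rows of Tables 1 and 3 leave a confirmed recurrence or secondary malignancy that is treated afterwards without a row. This is a drafting contradiction, not a chosen rule, and it should be corrected because it lies in the derivation of the primary event.

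Its size per patient is one event lost from the 184/245 count, with a censoring time that can equal, follow or precede the true event time. Its size for the trial depends on how many events are treated afterwards and on whether 5.1 is programmed literally. The documents give neither, so no power loss is claimed. The shares in steps 4 and 5 are assumptions that show mechanism only. The 2.5% margin by month 60 rests on the plan's own inputs plus uniform accrual and exponential drop-out.

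**What to change.** - **SAP 5.1.** Limit the therapy rule to subjects who receive anti-tumor therapy after randomization and before recurrence, secondary malignancy or death.
- **Event rows of Tables 1 and 3.** Word the condition as no anti-tumor therapy after randomization and before recurrence, secondary malignancy or death.
- **Conforming edits, eight rows.** Use the same limit in the no-therapy missed-scan rows of Tables 1 and 3 (two rows) and in the two parallel rows of each of Tables 5, 6 and 7 (six rows). There, at most a date or a sensitivity analysis is affected. Table 4 needs no change.

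The cost is SAP wording: one sentence, two event rows and eight conforming rows. It needs no new data and no change to the protocol definition, which it restores. It should be done before the event derivation is locked.
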